4.1 Care Settings

Influenza vaccinations and AEs will be identified in care settings of interest based on clinical guidance, as specified in Section 4.2 and 4.3. Table 2 defines the inpatient (IP), outpatient department and professional (OP/PB), and OP-ED settings used in this study.

Table 2. Care Setting Definitions

Care Settings	Definition
Inpatient (IP)	Hospital inpatient acute facility claims
Outpatient and Professional (OP/PB)*	Outpatient facility claims or Professional claims that contain at least one non-laboratory place of service**
Outpatient Emergency Department (OP-ED)†	Outpatient facility claims in ED

* Including all sources of professional claims (e.g., urgent care etc.)

** Independent laboratory place of service code = 81

† A subset of the OP/PB setting

The IP setting represents hospital inpatient acute facility claims. Hospital inpatient facility claims detail the care and services received by patients during the entire duration of inpatient care. Hospital claims may have more accurate diagnosis coding compared to professional claims, given that provider facilities are reimbursed based on the types of diagnosis coded, which reflect the level of treatment required.

The OP/PB setting represents all outpatient and professional services claims with non-laboratory places of service and captures the broad spectrum of outpatient care regardless of care setting or provider type. Claims with laboratory places of service are excluded, given that these claims often include “rule-out-diagnoses” that may not reflect existing or underlying conditions present in patients.

The OP-ED setting is a subset of the OP/PB setting and represents outpatient facility claims with services specifically provided in the ED, identified through place of service (POS) and revenue (REV) codes, in PB and OP settings, respectively.

4.2 Exposure

The study will focus on influenza vaccinations approved for use during the 2022-2023 influenza season extending from August 1, 2022 to July 31, 2023.² Any beneficiary with a relevant vaccine product code between August 1, 2022 and November 12, 2022 (vaccination cutoff date) will be included in the study population. The vaccination cutoff date is the latest date in which influenza vaccines administered will be eligible for inclusion in the study. The rationale for the vaccination cutoff date is further described in Section 5.5.1. For persons eligible for inclusion in the study, only the incident vaccine administration observed during the study period will be included.

Table 3 presents a list of the product-specific administration codes⁽²²⁾ that will be used to identify influenza vaccine exposures by vaccine type and vaccine group. Analyses will be performed across influenza vaccines overall, and by individual vaccine groups (as referenced in Section 5.5). The study will specifically focus on codes recommended for use in persons aged 65 years and older. Current Procedural Terminology (CPT)/Healthcare Common Procedure Coding System (HCPCS) codes will be used to identify influenza vaccines administered. The following list will be expanded to include any additional influenza vaccine codes approved as of the study initiation date.

² Based on the effective dates for influenza vaccine codes specific to the 2022-2023 influenza season.

Table 3. 2022-2023 Influenza Vaccine Exposure Code List and Classifications

Code Type	Code	Vaccine Name	Vaccine Type			Vaccine Group
			Vaccine Classification		Abbreviated	
CPT	90662†	Fluzone High-Dose Quadrivalent (2022-2023)	Inactivated	High-dose	IIV4-HD	High-dose
CPT	90674	Flucelvax Quadrivalent (2022-2023)	Inactivated	Cell-cultured	ccIIV4	Other
CPT	90682†	Flublok Quadrivalent (2022-2023)	Recombinant	Recombinant	RIV4	Other
CPT	90686	Fluarix Quadrivalent (2022-2023)	Inactivated	Standard (split virus)	IIV4	Other
		Flulaval Quadrivalent (2022-2023)				Other
		Fluzone Quadrivalent (2022-2023)				Other
		Afluria Quadrivalent (2022-2023)				Other
CPT	90688	Fluzone Quadrivalent (2022-2023)	Inactivated	Standard (split virus)	IIV4	Other
		Afluria Quadrivalent (2022-2023)				Other
CPT	90694†	Fluad Quadrivalent (2022-2023)	Inactivated	Adjuvanted	aIIV4	Adjuvanted
CPT	90756	Flucelvax Quadrivalent (2022-2023)	Inactivated	Cell-cultured	ccIIV4	Other

†CDC preferentially recommended influenza vaccines for use in persons aged 65 years and older³

Note: Assessment of AE incidence rates will be performed across approved influenza vaccines overall, and by high-dose and adjuvanted vaccine groups only. No further analyses will be performed restricted to the “other” vaccine grouping as this will likely not be sufficiently powered in this population.

4.3 Adverse Events

AEs of interest in the study are anaphylaxis, encephalitis or encephalomyelitis (including ADEM), GBS, and transverse myelitis. These events were selected due to their potential association with influenza vaccines based on literature review, experience with prior seasons’ influenza vaccines, and clinician consultation. AEs will be captured using International Classification of Diseases, 10th Revision, Clinical Modification (ICD-10-CM) diagnosis codes billed in claims.

The study will focus on incident AEs occurring during the observation period, defined as no prior occurrences of the AEs observed during the specified clean period. The clean period is the duration prior to the first AE occurrence during the observation period, during which persons with an observed AE will be excluded from the study population. This ensures that only incident cases of the event are captured. Cleaning occurs relative to the incident AE occurrence date, and within AE-specific care settings.

Table 4 displays the AEs included in the study and summarizes the medical diagnosis codes, care settings, risk and control intervals, and clean periods used in the study.

Table 4. Summary of AE Definitions

AE	AE Definition				
	ICD-10 CM codes	Care Settings*	Risk Interval**	Control Interval***	Clean Period†*
Anaphylaxis	T782XXA, T8052XA	IP,OP-ED	0 - 1 days	3-16 days	30 days
Encephalitis or Encephalomyelitis (including ADEM)	G0400, G0402, G0481, G0490, G053	IP	1 - 42 days	43-90 days	183 days
Guillain-Barré Syndrome	G610	IP (primary diagnosis position)	1 - 42 days	43-90 days	365 days
Transverse Myelitis	G373	IP, OP-ED	1 - 42 days	43-90 days	365 days

* Care setting definitions are specified in Section 4.1.

**Hypothesized period of elevated AE risk relative to vaccination date, during which incident AE occurrences are attributed to the vaccine. Extends from vaccine administration date through AE-specific risk interval.

***Follow-up time during the observation period following the risk interval. Specified relative to vaccination date.

†* Cleaning will occur relative to the incident AE occurrence date, and within AE-specific care settings.

5. Study Design

5.1. Study Population

The study will include eligible vaccinees enrolled in Medicare during the study period who receive an influenza vaccine and meet the inclusion and exclusion criteria below, regardless of AE occurrence. All eligible vaccinees will be used to estimate attributable risks (ARs), whereas a subset population with an observed AE occurrence during the observation period (case population) will be used to estimate IRRs.

Inclusion criteria

- (i) Beneficiaries must be enrolled in Medicare Part A (inpatient insurance) and Part B (outpatient and physician services insurance) FFS plans during the observation period, which extends from vaccination date through the earlier of the AE control period end, or any of the censorship criteria (i.e., disenrollment, subsequent influenza vaccination, study period end, or death). Definitions for the risk, control and observation period can be referenced in Section 5.4.
 - If a follow-up concomitant vaccines analysis is applicable, Part D insurance will also be required during the observation period to ensure comprehensive capture of concomitant vaccinations.
- (ii) Beneficiaries must have received an influenza vaccine during the study period and prior to the vaccination cutoff date (latest date vaccine administration will be eligible for inclusion in the study). Further information on the rationale for this cutoff is provided in Section 5.5.1.
- (iii) Beneficiaries will be required to have continuous enrollment in Medicare Parts A and B FFS from 365 days prior to influenza vaccination through the earlier of the observation period end, or any of the censorship criteria (i.e., disenrollment, subsequent influenza vaccination, or death).

- (iv) For the case population only, each case must have a record of an incident AE diagnosis during the observation period.

Exclusion criteria

- (i) Medicare beneficiaries less than 65 years of age at the time of influenza vaccination.
- (ii) Individuals that do not contribute *any* follow-up time to both risk and control intervals i.e. beneficiaries that meet any of the censorship criteria during the risk interval prior to accumulating time in the control interval will be excluded.
- (iii) Individuals vaccinated with multiple influenza vaccine brands on the same day or multiple influenza vaccinations (same/different brand) within 3 days of each other.
- (iv) People who received a diagnosis of the AE during the AE-specific clean period.

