- **Primary Objective:** To estimate the incidence rate of the following AEs: anaphylaxis, encephalitis or encephalomyelitis (including acute disseminated encephalomyelitis (ADEM)), GBS, and transverse myelitis after exposure to influenza vaccines in the risk interval, compared to the incidence rate of the AEs in the control interval. Assessment of AEs incidence rates will be performed for all influenza vaccine types combined together (overall), and for high-dose and adjuvanted vaccine groups separately. Vaccine groupings are presented in Table 3.
 - **Follow-Up Objective (if applicable):** If there is a statistically significant association in the primary analysis indicating a potentially increased rate of an AE in the risk compared to control interval, we will evaluate the potential contribution of concomitant (same-day) vaccination with at least one of five other vaccines to the elevated incidence rate for the given AE. The analysis for the specific outcome(s) with a statistically significant result will be stratified by concomitant vaccination status (influenza vaccination alone, and influenza vaccine *with any* same-day concomitant vaccination). Where sufficiently powered, follow-up analyses by combinations of concomitant vaccines may be performed.
 - Concomitant vaccines of interest are listed below.^{1(23, 24)} Table E1 can be referenced for associated vaccine code lists:
 - COVID-19 Bivalent (Pfizer-BioNTech, Moderna)
 - Pneumococcal (PCV15/20, PPSV23)
 - Hepatitis B
 - Tetanus (Tdap, tetanus, diphtheria (Td))
 - Shingrix

3. Data Sources

The study will be performed using the Medicare administrative claims database. The Medicare claims database includes well-defined longitudinal data that captures healthcare service utilization for millions of enrollees across multiple care settings including inpatient, outpatient-emergency department (OP-ED) and outpatient non-ED, professional services non-laboratory and laboratory, and pharmacy settings.

The Medicare Study will include CMS Medicare Shared System Data (SSD) to capture longitudinal healthcare information for persons aged 65 years and older in the study population. Medicare Fee-for-Service (FFS) Part A (inpatient) and Part B (outpatient and physician services) will be used to capture patient's vaccination history, healthcare services, health-related covariates, and diagnoses. Medicare

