5.4.1.1 Observation Period

The observation period length will be AE-specific. For each individual, the observation period will start from the day following influenza vaccination (except for anaphylaxis which will begin on the day of vaccination) and extend through the earlier of the end of the AE-specific control interval, study period end, or any of the specified censorship criteria (i.e., disenrollment, subsequent influenza vaccination).

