5.5.4 Follow-Up Inferential Analysis- Concomitant Vaccination Analysis

5.5.4.1 Incidence Rate Ratio (IRR) Estimation

The follow-up inferential analysis will only be performed for AEs for which a statistically significant elevated incidence rate ratio is observed from the primary analysis. This analysis will be implemented consistently with the primary analysis specified in Section 5.5.3.1, except the analysis will be conducted in two separate subgroups. One subgroup will include persons with an observed influenza vaccination *with any* concomitant (same-day) vaccination, and the other subgroup will include persons with influenza vaccination *without any* concomitant (same-day) vaccination. Where sufficiently powered, follow-up analyses may be performed by combinations of concomitant vaccines.

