*Captures vaccine combinations including hepatitis B (hepatitis B and A; hepatitis B and Hib).

†Captures vaccine combinations including tetanus (Tdap, Td, DTaP-HepB-IPV, DTaP-IPV-Hib, DTaP-IPV, DTaP-IPV-Hib-HepB). DTaP combinations used in pediatric populations are included to ensure comprehensive capture of concomitant vaccination in claims.

Note: COVID-19, hepatitis B, and PCV vaccines will be captured using CPT/HCPCS product and administration codes only; these vaccines are billed through the Medicare Part B benefit that uses CPT/HCPCS codes for billing. Shingrix and tetanus vaccines will additionally be captured using NDCs as these vaccines are respectively billed through the Medicare Part D benefit or through both Medicare Part B and D benefits; NDCs are used to bill to Part D.

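### The concomitant-vaccination follow-up is limited to Part D enrollees for the whole observation period, with no unstratified IRR in that subset to link its strata to the primary signal

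*Protocol*

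**What the plan says.** - **Primary population.** Section 5.1, criterion (iii): "Beneficiaries will be required to have continuous enrollment in Medicare Parts A and B FFS from 365 days prior to influenza vaccination". Part D is not needed.
- **Purpose of the follow-up.** Section 2, after a significant primary result: "we will evaluate the potential contribution of concomitant (same-day) vaccination with at least one of five other vaccines to the elevated incidence rate".
- **Follow-up population.** Section 5.1, criterion (i), sub-bullet: "If a follow-up concomitant vaccines analysis is applicable, Part D insurance will also be required during the observation period". The stated reason is complete capture of concomitant vaccines.
- **Follow-up model.** Section 5.5.4.1: "This analysis will be implemented consistently with the primary analysis specified in Section 5.5.3.1, except the analysis will be conducted in two separate subgroups". The subgroups are influenza vaccination with and without any same-day co-vaccination. The section does not mention Part D or an unstratified fit among Part D enrollees.
- **Start of observation.** Section 5.1(i) describes a period "which extends from vaccination date through the earlier of the AE control period end, or any of the censorship criteria", and the GBS example in Section 5.4.1 also starts on the vaccination date. Section 5.4.1.1 differs: "the observation period will start from the day following influenza vaccination (except for anaphylaxis which will begin on the day of vaccination").
- **Where co-vaccines are billed.** Section 10.1, note to Table E1: "COVID-19, hepatitis B, and PCV vaccines will be captured using CPT/HCPCS product and administration codes only", because these are Part B benefits. Shingrix and tetanus are the two that also need Part D drug codes.

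**The concern.** The signal comes from one population and the explanation from a subset of it. Suppose the primary IRR is elevated and the stratum IRRs look different. A reader will want to credit co-vaccination, or its absence. Part of the shift could instead come from dropping people without Part D, through a different IRR among them or simply through fewer cases. The plan contains no adjusted estimate that isolates that step.

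The length of the requirement is a second issue. Co-vaccination status is settled on one day, yet Part D must be held for up to 90 days. Anyone who loses Part D in between is dropped or has follow-up cut short, with no gain in classification.

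**Working it through.** The protocol gives no case count, power or Part D share for the follow-up, so there is no planned figure to reproduce.

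**1. Do the strata add up to the primary population?** Let f be the share of primary cases that meet the Part D rule. The two strata together hold the fraction f of the primary cases, so they equal the primary population only if f = 1.

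**2. Which days need Part D?** Status is defined on the influenza vaccination date (Sections 2, 5.5.2 and 5.5.4.1), which is day 0. A Part D claim on day 1 or later cannot change it.

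**3. Where does year end fall?** The vaccination cutoff is November 12, 2022 (Section 4.2). Table 4 sets risk days 1-42 and control days 43-90 for encephalitis, GBS and transverse myelitis.
- Vaccinated October 3: 28 days to October 31, + 30 to November 30, + 31 to December 31 = day 89, so January 1 is day 90.
- Vaccinated November 12: 18 days to November 30, + 31 to December 31 = day 49, so January 1 is day 50.

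For every vaccination between these dates, January 1 lies on days 50-90, always in the control interval. A Part D loss at year end would therefore fall in control time. Anaphylaxis is not affected: its control interval ends on day 16, and November 12 + 16 days is November 28.

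**4. Is day 0 inside the observation period?** For the three AEs with a day 1-42 risk interval:

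| Source | Days | Length | Day 0 covered |
|---|---|---|---|
| Sections 5.1(i) and 5.4.1 (GBS example) | 0-90 | 91 | yes, but in neither interval |
| Section 5.4.1.1 | 1-90 | 90 = 42 + 48 | no |

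For anaphylaxis, day 0 is covered under both. Section 5.1(i) refers to Section 5.4 for the definition, and that section holds both versions.

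**5. Illustrative loss of power (f assumed).** With one event per case and r = 42/90, the share of events in the risk interval is p = IRR·r / (IRR·r + 1 − r). Power = Φ(√(n·p(1−p))·ln IRR − 1.96). At IRR 1.5, p = 0.700/(0.700 + 0.533) = 0.568, and 80% power needs n = 195 cases. At IRR 2.0 it needs 71. Keeping f·n cases gives, for either IRR:

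| f (assumed) | Power in all Part D cases, before the split |
|---|---|
| 0.5 | about 51% |
| 0.7 | about 65% |
| 0.9 | about 76% |

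The split itself costs more. With f = 1 and half the cases co-vaccinated, each stratum has about 51%; with f = 0.7 it has about 38%.

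**6. How far could the restriction move the IRR?** Here let f be the Part D share of background events, with equal background rates. Then overall IRR = f·IRR(in) + (1 − f)·IRR(out). For an overall IRR of 1.5 with 1.0 inside Part D, IRR(out) = (1.5 − f)/(1 − f): 2.0 at f = 0.5, 2.67 at f = 0.7, 6.0 at f = 0.9. A complete disappearance needs a large difference between the groups unless f is moderate; a partial shift needs less.

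**The case against.** - **The restriction is open and has a reason.** It sits in the eligibility section. Without Part D, Shingrix and some tetanus doses would be missed and their recipients counted as influenza vaccine alone. This stands, and the restriction should stay in some form. A reader might infer that Section 5.5.4.1 contradicts Section 5.1. It does not: it refers to the model in 5.5.3.1, while eligibility is set in 5.1. It is only silent on Part D.
- **The key contrast is sound.** Both strata carry the same Part D rule and estimation is within person. A pooled IRR lies roughly between its stratum IRRs, so if both strata fall below the primary IRR, that points to the restriction or chance and not to co-vaccination. This stands. A reader might infer that the follow-up cannot meet its objective; the documents do not support that. What is missing is the step from the primary IRR to the strata.
- **A crude version is already available.** Section 5.5.2 plans counts and unadjusted rates for the follow-up, and the strata sum to the Part D subset. True, but the signal is declared on the adjusted IRR, and no adjusted counterpart is planned.
- **Disenrollment is a censoring criterion,** so a later Part D leaver may be censored and not dropped. The protocol does not say whether losing Part D alone counts. Either way cases or control time can be lost and nothing is gained.
- **Day 0.** A reader might infer that the rule skips the vaccination day for three AEs. Only Section 5.4.1.1 implies this; the criterion carrying the Part D rule starts on the vaccination date. Even under 5.4.1.1, only someone whose Part D began exactly on day 1 would be affected.

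**Conclusion.** The point holds in a limited form. The follow-up uses a Part D subset of the population that raised the signal, and no adjusted unstratified IRR in that subset is planned. Comparisons of the primary IRR with either stratum therefore mix two changes; the comparison between strata does not. Requiring Part D beyond the vaccination date does nothing for same-day capture and can cost cases or control time, most visibly at year end. Coverage on day 0 is ambiguous, and that ambiguity is probably of little practical weight.

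The size is not known from the documents. The f values of 0.5 to 0.9 and the resulting power of about 51% to 76% are assumptions for illustration, tied to a primary analysis with exactly 80% power. The true loss may be small, and it arises only if the follow-up is triggered.

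**What to change.** 1. In Section 5.1(i), require Part D on the influenza vaccination date in place of the whole observation period. Reconcile the start of the observation period across Sections 5.1(i), 5.4.1 and 5.4.1.1.
2. In Section 5.5.4.1, state the Part D restriction and report the unstratified adjusted IRR in the Part D subset beside the two strata, as their reference.
3. Optional: a sensitivity split in the full Part A/B population using only the Part B-billed co-vaccines (COVID-19, hepatitis B, pneumococcal). Its drawback is real: Shingrix and Part D-billed tetanus recipients would be placed in the influenza-alone stratum, and Section 1 names both among vaccines linked to some of these AEs.

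Items 1 and 2 cost a few sentences and one extra model fit for each AE and vaccine group that triggers the follow-up. Item 3 adds the two stratum fits again.

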5.5.2 Descriptive Analysis

Descriptive analyses will be performed for the primary and follow-up analyses. For each of the case populations, the descriptive analyses will summarize the cases (counts and percentages) and unadjusted outcome rates following influenza vaccination by risk and control intervals. Descriptive statistics will be summarized for influenza vaccines overall and by high-dose and adjuvanted vaccine groups. Statistics will be summarized overall and by the following characteristics.

- (i) Demographics: Age, sex, race/ethnicity, dual eligibility status, region³, urban/rural, area deprivation index (ADI)⁽³¹⁾, nursing home residency status
- (ii) Health status: Influenza diagnosis (defined by the ICD-10-CM code J10.X) in the 30 days prior to influenza vaccination
- (iii) Concomitant vaccines administered on the influenza vaccine administration date (as specified in Section 2)
- (iv) Baseline health characteristics (defined by ICD-10 codes) in the 183 days prior to influenza vaccination:
 - Prior hospitalization
 - Asthma
 - Blood disorders
 - Chronic lung disease
 - Diabetes
 - Heart disease
 - Kidney disorders
 - Liver disorders
 - Neurological or neurodevelopmental conditions
 - Malignant neoplasms
 - Immunocompromised status (as binary covariate)⁴⁽³²⁾
 - Charlson comorbidity index

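### Primary descriptive tables break cases down by same-day vaccine without requiring Part D, so Shingrix and, to a lesser degree, tetanus counts and percentages are expected to be understated

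*Protocol*

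**What the plan says.** **Population.** Protocol Section 5.1, inclusion criterion (i), sets the primary requirement: "Beneficiaries must be enrolled in Medicare Part A (inpatient insurance) and Part B (outpatient and physician services insurance) FFS plans during the observation period". A sub-bullet adds Part D in one case only: "If a follow-up concomitant vaccines analysis is applicable, Part D insurance will also be required during the observation period to ensure comprehensive capture". Section 3 describes Part D data as a supplementary source of vaccination history.

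**Tables.** Section 5.5.2 opens: "Descriptive analyses will be performed for the primary and follow-up analyses". For each case population the tables are to "summarize the cases (counts and percentages) and unadjusted outcome rates following influenza vaccination by risk and control intervals", overall and by listed characteristics. Item (iii) of that list is "Concomitant vaccines administered on the influenza vaccine administration date (as specified in Section 2". Section 2 names five vaccines: bivalent COVID-19, pneumococcal, hepatitis B, tetanus and Shingrix.

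**Billing.** The note under Table E1 in Section 10.1 says of COVID-19, hepatitis B and PCV that "these vaccines are billed through the Medicare Part B benefit that uses CPT/HCPCS codes for billing". It then says: "Shingrix and tetanus vaccines will additionally be captured using NDCs as these vaccines are respectively billed through the Medicare Part D benefit or through both". The last word refers to Parts B and D. Table E1 lists national drug codes only for Shingrix and tetanus.

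**The concern.** The protocol accepts that co-vaccination is not comprehensively captured without Part D, and it acts on this for the follow-up analysis. It then tabulates the same variable in a population that may lack Part D. It does not restrict the affected rows, provide a category for people whose status cannot be fully known, or flag the gap.

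What is at stake is how the tables are read. Section 1 names Shingrix and Tdap among the vaccines associated with some of these adverse events, alone or given with others. The follow-up analysis runs only for an event with a significantly elevated IRR (Section 5.5.4). Without such a signal, the rows under 5.5.2(iii) are the only co-vaccination results the study produces. A reader could not tell that two of the five vaccines are captured less completely than the other three.

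**Working it through.** The protocol states no capture figure, so there is none to reproduce. The check compares the sections and then does bias arithmetic on stated assumptions.

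**Which rows are affected**

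| Vaccine | Billing route (Table E1 note) | Capture depends on Part D? |
|---|---|---|
| COVID-19, hepatitis B, pneumococcal | Part B | No |
| Tetanus | Parts B and D | Partly |
| Shingrix | Part D | Yes, apart from any claim found through its CPT code in Table E1 |

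**Inputs, all assumed**
- u = share of the primary population without Part D: 10% to 40%.
- m = share of a vaccine's claims that go only to Part D: 1.0 for Shingrix, following the billing note; 0.25 to 0.75 for tetanus.
- Same-day uptake is the same with and without Part D.

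**Counts and percentages.** Captured share = 1 − u × m, so the shortfall is u × m.
- Shingrix: 0.10 × 1.0 = 10% to 0.40 × 1.0 = 40%.
- Tetanus: 0.10 × 0.25 = 2.5% to 0.40 × 0.75 = 30%.

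The percentage of all cases with the vaccine falls by the same proportion, because its denominator does not change. If people without Part D have k times the uptake of those with it, the Shingrix shortfall becomes uk / (1 − u + uk). This equals u at k = 1 and is smaller when k is below 1.

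**Rate in the co-vaccinated stratum.** A missed person leaves both the case count and the person-time of that stratum. If the event rate among co-vaccinated people does not depend on Part D, the observed rate equals the true rate at any u: a true rate of 2.0 stays 2.0. If co-vaccinated people without Part D have f times the rate of those with it, observed/true = 1 / [(1 − u) + u × f]. At u = 25%:
- f = 0.5: 1 / (0.75 + 0.125) = 1.14.
- f = 2: 1 / (0.75 + 0.50) = 0.80.

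The direction is therefore not fixed.

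**Rate in a no-co-vaccination stratum, if one is shown.** Missed people move into it. With co-vaccinated share c, a true rate of 1 without co-vaccination and 2 with it, and m = 1, the observed rate is [(1 − c) + 2cu] / [(1 − c) + cu].
- c = 0.5%, u = 10%: 0.996 / 0.9955 = 1.0005.
- c = 5%, u = 40%: 0.99 / 0.97 = 1.021.

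The contamination exists, but it is slight over these assumed values.

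**The case against.** The strongest reply is that nothing inferential depends on these rows. Co-vaccination status does not enter the primary IRR model, the AR or the rule that triggers the follow-up analysis. The one objective that uses it is the follow-up, where Part D is required and which has its own descriptive tables. That stands, and it limits the point to descriptive tables.

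A second reply is that table layout belongs to the analysis plan or table shells. This stands in part. Section 5.5.2 does not specify an any/none row, or say that people without Part D are coded as unvaccinated, so neither can be charged to the protocol as written. But the protocol itself fixes both the population and the tabulated variable, and together they conflict with its own reason for requiring Part D.

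Third, a reader might infer that Shingrix is not captured at all without Part D. The documents do not go that far: Table E1 also lists a CPT code for Shingrix, so a Part B claim carrying it would be found. Tetanus is billed partly to Part B.

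Fourth, the size rests on assumptions. That is correct. In particular, same-day Shingrix uptake may well be related to having the benefit that pays for it.

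**Conclusion.** The point holds for counts and percentages. As the protocol stands, the primary Shingrix figures, and to a lesser degree the tetanus figures, are expected to be understated by about u × m. On the assumed ranges this is 10–40% for Shingrix and 2.5–30% for tetanus, if uptake is unrelated to Part D. The rows for COVID-19, hepatitis B and pneumococcal vaccines are not affected.

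A reader might also infer that the risk- and control-interval rates are understated. That does not follow, because missed people leave numerator and person-time together. Stratum rates are open to misclassification with no fixed direction. Only a rate over a common or complete denominator would fall in proportion, and the protocol does not describe one. Any group labelled as having no co-vaccination would include some co-vaccinated people.

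No IRR, AR or follow-up decision changes. The point is minor, but worth correcting because it alters reported numbers and costs little.

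**What to change.** In Section 5.5.2(iii), report the primary Shingrix and tetanus rows, and any row for any or no concomitant vaccine, among people who meet the Part D requirement already in Section 5.1, inclusion criterion (i). Show everyone else in a separate row labelled *no Part D: not fully ascertainable*. Showing these rows by Part D status would serve equally well. Reusing the Section 5.1 requirement avoids a second Part D definition and puts these rows on the same capture standard as the follow-up tables. Keep the Part B-billed vaccines in the full population.

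The cost is a Part D enrolment flag, which the follow-up analysis would need in any case, and an additional table row. The downside is smaller denominators for the affected rows. No inferential analysis changes.
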